[figure not shown]

pulseOx **Pulse oximetry as a screening test for congenital heart disease in newborn babies.**

PROTOCOL

The Pulse Ox Study aims:

- To develop pulse oximetry (PO) as a feasible screening tool for congenital heart disease (CHD) in newborn babies.
- To determine the accuracy (sensitivity, specificity, predictive values, and likelihood ratios) of PO for diagnosing critical and serious CHD in newborn, using echocardiography / clinical follow up / congenital malformation registries' data as reference standards.
- To determine the psychosocial effect of PO as a screening method among parents and acceptability to health professionals.
- To compare the cost and cost effectiveness of PO and other screening tests (routine neonatal clinical examination and antenatal screening) for improving outcomes of CHD in the newborn using model based economic evaluation.

All women booking into six large obstetric units, in the West Midlands area, will be invited to participate. The study aims to recruit 20,000 women over 12 months for the assessment of test accuracy and acceptability. The main analysis for diagnostic accuracy will estimate sensitivity, specificity, predictive values, likelihood ratios and their confidence intervals. Using multivariable logistic regression analysis, predictive probabilities for various combinations of history, antenatal tests and oximetry results will be generated.

Pulse Ox Study Management Committee

Chief Investigator

[name]
Birmingham Women's Hospital

Midwifery

[name]
Birmingham Women's Hospital

Clinical Co-investigators

[name]
Consultant in Obstetrics and Gynaecology
Birmingham Women's Hospital

Psychology

[name]
University of Aston

[name]
Paediatric Cardiologist
Birmingham Children's Hospital

Health Economics
[name]
University of Birmingham

Systematic Reviewer
[name]
Birmingham Women's Hospital

Statistics

[name]
University of Birmingham
[name]
University of Birmingham

Study Management

[name]
[name]
[name]
University of Birmingham

Study Steering and Data Monitoring and Ethics Committee

For interim analysis and response to specific concerns:

[name] [name], Academisch Medisch Centrum

[name], Little Hearts Matter

[name], University of Birmingham

[name], Sunderland Royal Hospital

[name], University of Oxford

Pulse Ox Study Office

The University of Birmingham Clinical Trials Unit,
Division of Medical Sciences, [name], University of Birmingham

1.0 Submitted to MREC

- 1.1 Incorporates MREC comments
- 1.2 Amendment number 1 – Minor - Administrative changes
- 1.3 Amendment number 2 – Minor - Administrative changes

2.0 Amendment Number 3 – Substantial – Change of eligibility criteria to include babies with extracardiac manifestations of CHD; submission of acceptability questionnaire; submission of Participant Information Booking Flyer, GP Poster and Participant Information Video; minor administrative changes.

3.0 Amendment Number 4 – Substantial – Clarification on data collection and administration of the acceptability questionnaires; clarification on consent procedure; definitions of critical and serious CHD

4.0 Amendment Number 5 – Substantial – Clarification and changes to the methods and analysis of acceptability to health professionals

- 4.1 Incorporates MREC comments with inclusion of staff information sheets. In addition, version number correction of previously submitted staff acceptability questionnaire

Funding Body

NHS Research and Development Health Technology Assessment Programme

Sponsor

The University of Birmingham is the sponsor. [name], Consultant Neonatologist, Birmingham Women's Hospital, is the Chief Investigator.

The University of Birmingham is responsible for obtaining necessary approvals and for safety monitoring, the Study Management Committee is jointly responsible for overseeing good clinical practice and the Investigators are responsible for obtaining informed consent and care of the participants.

CONTENTS

1. BACKGROUND	1
1.1. Clinical Context.....	1
1.2. Literature review	1
1.2.1 Accuracy of PO as a screening test for CHD in newborns	1
1.2.2 Evidence on effectiveness of early intervention for congenital heart anomalies.....	2
1.2.3 Evidence on cost effectiveness of PO as a screening test for CHD	3
1.3. Objectives of the Pulse Ox Study	3
2. STUDY DESIGN	4
2.1. Brief summary	4
2.2. Overview.....	4
2.3. Test accuracy study design	5
2.4. Large, simple study: minimal extra workload	6
2.5. Setting	6
3. ELIGIBILITY.....	6
3.1. Eligibility criteria for the test accuracy study	6
3.1.1 Inclusion criteria.....	6
3.1.2 Exclusion criteria.....	6
3.1.3 Inclusion of babies with suspected CHD from antenatal ultrasound.....	6
3.2. Recruitment of participants	7
3.3. Consent	8
3.4. Organisation of Recruitment	8
4. TESTS AND PROCEDURES.....	8
4.1. The index test	8
4.2. Clinical examination.....	9
4.3. The reference standard	9
4.3.1 Echocardiography.....	10

1. BACKGROUND

1.1. Clinical Context

CHD is the commonest group of congenital malformations and affects 7-8/1000 live born newborns (1;2). It contributes to 3% of all infant mortality and 46% of deaths from congenital malformations with most deaths occurring in the first year of life. A significant proportion of these children require surgery in the first year. Survival rates for infants with CHD have increased dramatically in recent years and over 80% of children born with CHD will survive to the age of 16 years; this is due largely to improvements in surgical techniques (3). Although the commonest types of CHD do not usually develop serious problems in the neonatal period, there are a number of important cardiac defects which, if undiagnosed, can present with potentially life-threatening cardiovascular collapse in the first few days of life. Although individually less common, when taken together, these lesions contribute significantly to death in infancy. As death or poorer outcome following surgery is much more likely if cardiovascular collapse occurs prior to diagnosis, timely recognition of these cardiac defects prior to collapse is vital in order to improve outcome.

Currently in the UK, all newborn babies undergo a routine screening examination, usually in the first 24 hours after birth, during which, among other things, a careful assessment of the cardiovascular system is undertaken. However, it is estimated that over 50% of babies with undiagnosed CHD failed to be picked up by routine neonatal examination. In addition, some hospitals are deferring this examination and it is then performed by the GP – sometimes up to 10 days after birth. This increases the risk of a baby with CHD presenting with acute deterioration before the screening exam has taken place. Antenatal screening for CHD in high risk pregnancies by fetal echocardiography has been developed and in experienced hands appears a useful technique (4), however a recent HTA assessment review of *routine* ultrasound screening in pregnancy concluded that detection rates for CHD were low (5). The need for an accurate, simple, non-invasive test for CHD in the early neonatal period has led a number of investigators to examine the use of PO and although results are encouraging, as we demonstrated in our systematic review (see below), there is a clear need for a larger, robust, well conducted study to confirm the value, acceptability and cost effectiveness of such a screening programme.

This large multi-centre study will determine the accuracy of PO screening for diagnosing critical and serious CHD in newborns. It will evaluate the acceptability of PO to both parents and health professionals. The study will also assess the costs and cost effectiveness of utilising such screening in combination with clinical examination in the early detection of potentially life-threatening CHD.

1.2. Literature review

1.2.1 Accuracy of PO as a screening test for CHD in newborns

The NHS Research and Development Health Technology Assessment Programme (HTA) commissioned a systematic review of screening for CHD in newborns which was published in 2005 (6). This report included 4 studies examining the role of PO as a screen for CHD in newborns. In 2007, we published a further systematic review of this screening test (7). An extensive search (from database inception to 2006) to retrieve primary and review articles was performed and from a total of 233 citations, 8 relevant studies - 4 more than those included in the previous HTA report (6) - were identified (Table 1). A careful and detailed analysis of the findings were summarised by meta-analysis using the bivariate model, which allows for some variation in threshold. The review can be summarised as follows:

- The quality of the studies was varied in both design and conduct: six studies recruited newborns consecutively (8-13); two were case control studies (14;15) - a

design that biases the results by overestimating the diagnostic odds ratio; two were not prospective (14;15); three studies raise concerns about spectrum bias due to exclusions of antenatally diagnosed cases (10;11;13); none calculated power *a priori*; and sample size was often inadequate to precisely estimate sensitivity.

- There were various thresholds for abnormality of test results (Table 1).
- Only one study explored the added value of PO above the accuracy achieved through clinical examination. The combination of PO and clinical examination had a sensitivity of 76.9% (95% CI, 46.2% to 95%) and specificity of 99.9% (95% CI, 99.8% to 100%) (8).
- None of the studies evaluated acceptability of testing to parents and the psychosocial impact of false positive results or identification of non critical CHD.
- None of the primary studies provided information on cost and cost effectiveness.

Table 1 The accuracy of PO for diagnosing CHD in asymptomatic newborns

Test	No. of patients	Sensitivity % (95% CI)	Specificity % (95% CI)	False Positive Rate% (95% CI)	Timing of the test after birth
Most commonly used threshold					
saturation* ≤95% foot	11281	60 (14.7-94.7)	100 (100-100)	0	After 24 hrs or discharge
saturation* ≤95% foot or hand	2114	66.7(9.4-99.2)	99.9(99.7-100)	0.1(0-0.3)	As close to discharge as possible
saturation* ≤ 95% foot	3262	96.8(73.6-100)	99.7(99.5-99.9)	0.3(0.1-0.5)	Between 6 and 12 hours
saturation§ <95% foot	5626	25(12.7-41.2)	99.6(99.4-99.7)	0.4(0.3-0.6)	Between 2 hrs and discharge
saturation* ≤ 95% foot	5292	66.7(9.4-99.2)	100(99.9-100)	0(0-0.1)	>24 hrs
saturation§ <95% hand or foot	5211	30.8(9.1-61.4)	100(99.9-100)	0(0-0.1)	Prior to discharge
saturation* <95% foot	2733	75(57.8-87.9)	87.9(86.6-89.1)	12.1(10.9-13.4)	<6 hours of life, at 24hrs of life and/or at discharge
saturation* <95% foot	266	89.4(79.4-95.6)	99(96.4-99.9)	1(0.1-3.6)	12 hours (controls) or prior to surgery (cases)
Most accurate threshold					
saturation* <95% in both limbs or a differential of >3%	266	98.5(91.8-100)	96(92.3-98.2)	4(1.7- 7.7)	12 hours (controls) or prior to surgery (cases)
Summary estimate	35785	63.4(38.7-82.5)	99.8(99-100)	0.2(0-1)	summary using bivariate method of meta analysis

* functional oxygen saturation § fractional oxygen saturation

The highest sensitivity seemed to be obtained with a cut off level of functional saturation <95% in both limbs or a differential of >3% in saturation between foot and right hand (15). The false positive rate could be influenced by the age of screening. Performance of the test after 24 hours of birth seems to have the highest specificity (100%) with the lowest false positive rates (10;11). These findings need further evaluation; there are potential concerns that some babies with CHD may present with clinical deterioration before 24 hours and therefore be missed by later screening. There is a clear need for an appropriately designed large test accuracy study evaluating PO as a screening tool for CHD in newborns.

1.2.2 Evidence on effectiveness of early intervention for congenital heart anomalies

In recent years, there has been a significant increase in survival of children with CHD. Developments in ultrasonography have resulted in more precise diagnosis without the

need for invasive procedures, and advances in surgical techniques mean that cardiac conditions which were considered lethal (e.g. hypoplastic left heart) are now routinely offered surgery. However, some cardiac lesions present with acute cardiovascular collapse or death prior to diagnosis. It is clear that if a baby presents with a clinical deterioration before surgery then this leads to worse outcomes (16). It is this group of babies in particular who would benefit from early detection via an appropriate and timely screening technique. This study will pay particular attention to timeliness of PO testing.

1.2.3 Evidence on cost effectiveness of PO as a screening test for CHD

None of the studies identified in the above systematic review had any cost or cost effectiveness data. The HTA systematic review of Knowles *et al* (6) reported the use of a decision analytic model to estimate the cost-effectiveness of clinical examination either alone, or with PO, or with screening echocardiography. The outcome of interest was timely diagnosis of life-threatening CHD, with clinically significant CHD as a secondary outcome. Data from the Northern Region study (1) were used to estimate prevalence of defects and probabilities of outcomes. Unit cost data was obtained by direct observation of a small number of screening tests, contact with manufacturers and published standard costs of management of CHD cases.

Using this model to estimate cost-effectiveness in a hypothetical population of 100,000 live born infants, it was estimated 82 cases of life-threatening CHD would be identified using a combination of PO and clinical examination, compared with 39 cases by clinical examination alone. The costs of the screening programmes would be £480,000 and £300,000 respectively, or an additional cost of £4,900 per additional timely diagnosis for the combined strategy. The cost of using screening echocardiography alongside clinical examination was prohibitive at £4.5m per additional timely diagnosis with a four-fold higher false positive rate. Although sensitivity analysis showed the findings are robust to many parameters, detection rates and screening tests costs influence cost-effectiveness greatly. The model assumes the screening tests are performed at 24 hours of age, whereas, if this test were to become routine, it would most likely be performed much earlier. The time of diagnosis is a major difference from this study: detection rates influence the model yet no data exists to demonstrate the impact of timing of diagnosis on test performance.

1.3. Objectives of the Pulse Ox Study

The objectives of the study have been framed to assess PO for screening for CHD in newborn babies in a hierarchical fashion, based on methodologically robust frameworks for evaluation of diagnostic tests outlined by Guyatt *et al* (17) and Fryback and Thornbury (18), as follows.

- To develop PO as a feasible screening tool for CHD in newborn babies.
- To determine the accuracy (sensitivity, specificity, predictive values, and likelihood ratios) of PO for diagnosing critical and serious CHD in newborns, using echocardiography / clinical follow up / congenital malformation registries' data as reference standards (see Appendix E for CHD definitions).
- To determine the psychosocial effect of PO as a screening method among parents and acceptability to health professionals.
- To compare the cost and cost effectiveness of PO and other screening tests (routine neonatal clinical examination and antenatal screening) for improving outcomes of CHD in the newborn using model based economic evaluation.

2. STUDY DESIGN

2.1. Brief summary

The current neonatal screening for CHD involves a clinical examination undertaken either by a trained health professional prior to discharge from hospital, or by a GP up to 10 days following delivery. The study will evaluate screening using PO undertaken by a midwife within 24 hours of birth. The primary analysis will be accuracy of PO in detecting life-threatening CHD. A comparison of the performance of PO either against, or in addition to, antenatal screening will be made by multivariable logistic regression analysis; another with postnatal clinical examination will be made by decision analytic modelling. The study will also assess parental perception and acceptability to healthcare staff. A cost-effectiveness analysis comparing different screening strategies will be undertaken, using direct study data where possible, in a model-based economic evaluation.

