2.2. Overview

[figure not shown]

Figure 1: Flow chart of study organisation

This study will assess the accuracy, effectiveness and efficiency of PO in a delayed-type cross-sectional accuracy study. First, PO will be performed soon after delivery in all cases, which will have the advantage of identifying potentially serious low oxygen saturations in a timely fashion before symptoms are apparent. Integrating PO into the assessments performed routinely by the midwife when mother and baby are transferred from the delivery suite to the post-natal ward will make this design practicable and achieve maximum recruitment. Testing will occur early but over a range of times within the first 24 hours after birth (usually within 3-6 hours) or before discharge, allowing analysis of the optimum time for PO screening. After conducting PO, we will use different reference standards for test positive and test negative cases: echocardiography for the former and follow-up for the latter.

In this design, it would be unlikely that the subsequent clinical examination could be performed independently of the PO results, as midwives would want to alert the medical staff to a low saturation. This precludes a direct comparison of PO against clinical examination, as the latter would be prone to work-up bias. This comparison will be made through decision-analytic modelling using unblinded and historical data for input and appropriate sensitivity analyses conducted.

Clearly, in the presence of a feasible and accurate CHD screening strategy, there will be a need to consider the cost-effectiveness. The cost-effectiveness of PO in combination with postnatal clinical examination will be evaluated against examination alone and examination and antenatal screening, in a model-based analysis. Two systematic reviews of the performance of antenatal screening for CHD in first trimester (4) and second trimester (19) have been performed. Data on this group will be collected as part of our study. Using directly obtained information on outcomes and costs from a large number of babies in a real-life setting, the implications of all methods of identification of CHD will be modelled, thereby improving the generalisability of the results.

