* For the purposes of this study, "serious" adverse events are those occurring in either subjects or testers which are fatal, life-threatening, disabling or require some form of medical or surgical treatment.

difficulties in interpretation as the focus will be only on clinically significant CHD which is likely to be detected equally well by both reference standards.

One of the conclusions that arose from the recent systematic review is the need for a large well conducted study, aimed at improving the precision of the sensitivity estimate of the test. The sensitivity of PO as a screening test for CHD varied between 25% (95% CI, 13% to 41%) (12) and 98.5% (95% CI, 91.8% to 100%) (15) in previously conducted studies. The performance of the test, particularly estimates of sensitivity depends on the absolute number of patients with disease. Thus there is imprecision of the sensitivity estimates due to the low prevalence of CHD in relatively small studies. This study has been planned to be large enough to achieve good precision, as shown in section 6.1.

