5.2. Primary outcome measures

These will be the accuracy of each index tests for detection of CHD, expressed as sensitivity, specificity, positive and negative predictive values and positive and negative likelihood ratios, together with 95% confidence intervals.

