Using multivariable logistic regression analysis, predictive probabilities will be generated for various combinations of history, antenatal tests and oximetry results (43) Historical features to be included in the regression model will include gestational age (35-37, >37 weeks' gestation), antenatal scan findings, clinical examination (although this is likely to be affected by workup bias) and family history of CHD. In statistical terms, logistic modelling will aim to derive a diagnostic regression function, i.e. probability of CHD given test result. The analysis will be performed with presence or absence of CHD verified by reference standard as the binary dependent (outcome) variable. The models will allow a direct estimation of the post-test-combination disease probabilities that is needed for decision-making and for decision-analysis. Models of varying complexity may be compared through the familiar receiver operating characteristic (ROC) analyses. More importantly, the clinical situation where some information is already acquired, such as antenatal ultrasound or presentation with symptoms prior to undertaking PO, will be mirrored. In this way, for various index test results conditional disease probabilities will be generated directly taking into account any overlap of information that may exist between tests. This approach evaluates the extent to which the findings of the index tests add value to the babies' presentation. Its output is transparent, and is likely to enable production of simple clinical algorithms based on probabilities. The advantages of tackling diagnostic problems with logistic regression modelling are well known (44;45). The limitation associated with the regression approach lies mainly in its generalisability to other data sets or clinical practices. The recommended techniques, such as bootstrapping to enhance generalisability and estimate the amount of shrinkage will be applied for model validation (46;47). It is anticipated that the sample will comfortably meet the recommended events per variable rule to avoid overfitting the models (48-50) even if some data were missing. In a sensitivity analysis, missing data will be estimated by multiple imputation and maximum-

likelihood methods, as appropriate, to explore the potential bias and reduced statistical power associated with listwise deletion (51).

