APPENDIX E: DEFINITIONS OF ECHOCARDIOGRAPHIC FINDINGS

Normal	No echocardiographic abnormalities
Non- Significant	No clinical signs (e.g. murmur, thrill, pulse abnormalities, hepatic enlargement) No symptoms Small patent ductus arteriosis (PDA) or small inter-atrial communication (patent foramen ovale (PFO), atrial septal defect (ASD) or muscular ventricular septal defect (VSD)) Mildly abnormal turbulence at branch Pulmonary Artery Echocardiographic findings no longer detected at 6 months
Significant	Small patent ductus arteriosis (PDA) or patent foramen ovale (PFO) or muscular ventricular septal defect (VSD) Mildly abnormal turbulence at branch Pulmonary Artery Above where echocardiographic findings persist for longer than 6 months of age Any cardiac lesion which requires regular monitoring beyond 6 months or drug treatment but does not fall into serious or critical category.
Serious	Any cardiac lesion not defined as critical which requires intervention (cardiac catheterisation or surgery) within 1 year of age
Critical	All infants with hypoplastic left heart, pulmonary atresia with intact ventricular septum, simple transposition of the great arteries or interruption of the aortic arch and all infants dying or requiring surgery within the first 28 days of life with the following conditions: coarctation of the aorta, aortic valve stenosis, pulmonary valve stenosis, tetralogy of Fallot, pulmonary atresia with ventricular septal defect, or total anomalous pulmonary venous connection.

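### The primary target condition is not fixed: sections 1.3, 2.1, 5.1, 5.2 and 6.3 name it differently, and the choice decides both exposure to differential-verification bias and precision

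*Protocol*

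**What the plan says.** The protocol names the condition to be detected in several ways.

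- **Section 1.3 (objective):** the accuracy "of PO for diagnosing critical and serious CHD in newborns", with a pointer to Appendix E. The opening summary and section 1.1 agree.
- **Section 2.1:** "The primary analysis will be accuracy of PO in detecting life-threatening CHD".
- **Section 5.1:** after accepting that two reference standards can bias accuracy, it says "the focus will be only on clinically significant CHD which is likely to be detected equally well by both reference standards".
- **Section 5.2 (primary outcome):** "These will be the accuracy of each index tests for detection of CHD", with no severity limit.
- **Section 6.3 (regression):** "presence or absence of CHD verified by reference standard as the binary dependent (outcome) variable", again with no limit.

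Appendix E has five grades: Normal, Non-significant, Significant, Serious and Critical. Serious is "Any cardiac lesion not defined as critical which requires intervention (cardiac catheterisation or surgery) within 1 year of age". Significant is a lower grade. It covers small lesions such as a PDA, PFO or muscular VSD that persist past 6 months, and also "Any cardiac lesion which requires regular monitoring beyond 6 months or drug treatment but does not fall into serious or critical category". Life-threatening is not a grade.

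Verification is differential. Section 2.2 uses "different reference standards for test positive and test negative cases: echocardiography for the former and follow-up for the latter". Section 6.5 adds that screen negatives are not followed further by the study itself and rely on the anomaly register.

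**The concern.** The labels are not synonyms in this document. Section 1.2.3 describes an earlier model in which life-threatening CHD was the outcome of interest and clinically significant CHD a separate secondary outcome. Appendix E places Significant below Serious and Critical. Section 5.3.2 defines the false-negative and true-negative groups by CHD without a severity limit, and the case report form in Appendix D lists ASD, PDA and VSD as types of CHD without asking for a grade.

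Two things are at stake. First, the same data give different sensitivities and predictive values under each label, and the protocol does not say which is primary. Second, section 5.1 claims to escape the verification problem for sensitivity and specificity only because of a severity restriction, and section 5.2 as worded drops it.

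**Working it through.** **1. Reproducing the plan's own figures.** Inputs from section 6.1: N = 20,000, true sensitivity 75%, one-sided 2.5%, exact binomial limits, random number of cases.

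Let D ~ Binomial(N, prevalence) be the number of cases and x ~ Binomial(D, 0.75) the true positives. The lower limit is L(x, D) = the 2.5% quantile of Beta(x, D − x + 1). Power against p0 is the probability that L exceeds p0, summed over D and x.

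Sensitivity ruled out with 80% power:

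| N | 5 per 1000: computed (stated) | 2 per 1000: computed (stated) |
|---|---|---|
| 20,000 | 61.4% (61%) | 52.4% (52%) |
| 25,000 | 63.0% (63%) | 55.1% (55%) |
| 30,000 | 64.1% (64%) | 57.0% (57%) |

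All six agree, so the sensitivity calculation is sound. What is missing is the condition that it refers to.

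**2. Which target do the prevalences describe?** Section 4.3.1 uses 5 per 1000 and expects 9 per 1000 to have echocardiography, 40–50% of them with clinically significant CHD. This fits: 5 × 0.75 + 995 × 0.005 = 3.75 + 4.975 = 8.725 per 1000, and 3.75/8.725 = 43%. Section 6.1 supports the same prevalence with a figure of 6 per 1000 for moderate to severe CHD, a further label. No prevalence is given for critical plus serious CHD. The only figure tied to life-threatening CHD is in section 1.2.3: 82 cases identified per 100,000 in a model. That is 0.82 per 1000, and as a detection count it is a lower bound on prevalence.

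**3. Precision by label**, with N = 20,000 and sensitivity 75%:

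| Prevalence per 1000 | Expected cases | Ruled out at 80% power | Power to exceed 61% |
|---|---|---|---|
| 0.82–1.1 (assumed, life-threatening) | 16–22 | 38–43% | 14–20% |
| 2 | 40 | 52% | 40% |
| 5 | 100 | 61% | 82% |
| 7.5–8 (any CHD; section 1.1 gives 7–8) | 150–160 | about 64% | 95–96% |

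The last row holds only if sensitivity stays at 75% for minor lesions, which nothing in the protocol supports.

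**4. Direction of the bias under a broad target.** Suppose echocardiography finds every minor lesion in test positives and follow-up finds a fraction f of those in test negatives. Then apparent sensitivity = TP / (TP + FN_major + f × FN_minor). For any f below 1 this exceeds the true value.

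Illustration with assumed inputs that are not in the protocol: 2 per 1000 critical or serious (40 cases, sensitivity 75%), plus 5 per 1000 minor lesions (100), of which oximetry flags 5%, and f = 0.25.

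- TP = 30 + 5 = 35. True FN = 10 + 95 = 105. Observed FN = 10 + 0.25 × 95 = 33.75.
- True sensitivity 35/140 = 25%; apparent 35/68.75 = 51%.
- With specificity 99.5%, FP = 0.005 × 19,860 = 99.3, so test negatives number 20,000 − 35 − 99.3 = 19,865.7. True NPV = 1 − 105/19,865.7 = 99.47%; apparent 1 − 33.75/19,865.7 = 99.83%.
- PPV = 35/134.3 = 26% whatever the value of f. For critical or serious lesions alone it is 30/134.3 = 22%. The difference comes from the change of target, not from bias.

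With oximetry flagging 0.5% to 25% of minor lesions and f from 0.1 to 0.5, true sensitivity runs from 22% to 39% and apparent sensitivity from 34% to 76%. Within each combination the apparent value is the higher. This shows direction only.

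**The case against.** The strongest reply is that the target is settled and the other wordings are shorthand. The objective is stated consistently in three places, section 1.3 points to Appendix E, section 2.1 is only a brief summary, and CHD is the document's general abbreviation. Section 5.1 discusses differential verification openly and restricts the focus immediately before section 5.2. If clinically significant there means critical plus serious, its argument covers the case.

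This is a fair reading and probably the intended one, but no sentence says so, and Appendix E uses Significant for a lower grade. Section 2.1 is also the sentence that names the primary analysis.

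It can also be said that follow-up draws on several sources, that clinical signs lead to echocardiography whatever the oximetry result, and that section 4.4 expects no more than 5% of late-presenting cases to be missed. That helps for lesions that present. It says little about small lesions in babies without signs.

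A reader might infer that broader labels also inflate PPV. They do not: test positives all have echocardiography, and a higher PPV for a broader target is a different quantity. Section 5.1 says that both predictive values escape bias. For NPV this holds only if it is read as performance against follow-up, not as an NPV for all CHD.

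**Conclusion.** The point holds. The protocol does not fix one target condition for its primary accuracy analysis, and its labels lead to materially different analyses.

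Under unrestricted CHD, or if clinically significant includes the Appendix E Significant grade, sensitivity and NPV would be biased upward relative to their true values for that target. This assumes that echocardiography finds minor lesions more completely than register follow-up does. The documents give no figure for the size.

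Under a narrower label the cost is precision: power to exceed 61% falls from about 82% at 5 per 1000 to 40% at 2 per 1000, and to 14–20% at an assumed 0.8–1.1 per 1000.

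Two stronger readings are not supported. The life-threatening label adds no verification bias of its own; it only reduces the number of cases. Nor do the documents show that the study's sensitivity will be inflated: if the analysis keeps to critical plus serious CHD, the argument in section 5.1 applies.

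**What to change.** - Use critical plus serious CHD as graded in Appendix E, already the stated objective, as the single primary target in sections 2.1, 5.1, 5.2 and 6.3, including the regression outcome.
- State that Significant and Non-significant findings count as not diseased in the primary two-by-two table, and report them descriptively.
- Label any sensitivity or NPV for a broader target as secondary and subject to differential verification.
- In section 6.1, state which target the 5 and 2 per 1000 refer to. If critical plus serious CHD is rarer than 5 per 1000, restate the sensitivity that can be ruled out; at 2 per 1000 overall that would be 52%.

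The cost is wording in five sections and possibly a restated power figure. The real downside is fewer cases and wider intervals than under any CHD. For example, the exact 95% interval is 59–87% for 30 of 40 detected, against 65–83% for 75 of 100. The events-per-variable statement in section 6.3 should be rechecked against the smaller count.
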